12.7 Follow up Procedures for Adverse Events

The investigator may be asked to provide follow-up information to the GW PVD for any AEs reported.

AEs considered related to the IMP by the investigator or the sponsor should be followed up until resolution or the event is considered stable.

It will be left to the investigator's clinical judgment whether or not an AE is of sufficient severity to require the patient's removal from treatment. A patient may also voluntarily withdraw from treatment due to what he or she perceives as an intolerable AE, further details of withdrawal are presented in [Section 10](#). If either of these occurs, the patient must undergo an end of treatment assessment and be given appropriate care under medical supervision until symptoms cease or the condition becomes stable.

12.8 Potential Cases of Drug Induced Liver Injury

All investigational sites are required to submit to the GW PVD the laboratory results for any patient after randomization that meet the criteria for the selected laboratory parameters as follows:

- ALT or AST $>3 \times$ ULN **and** (TBL $>2 \times$ ULN **or** INR >1.5).
- ALT or AST $>3 \times$ ULN with the appearance of fatigue, nausea, vomiting, right upper quadrant pain or tenderness, fever, rash, and/or eosinophilia ($>5\%$).
- ALT or AST $>8 \times$ ULN.
- ALT or AST $>5 \times$ ULN for more than two weeks.

These reports must be sent to the GW PVD using the same fax number for SAE reporting within 24 hours of becoming aware of the results. In addition, please send a copy of the patient's baseline laboratory results with all reports to GW PVD.

Abnormal values in AST and/or ALT concurrent with abnormal elevations in TBL that meet the criteria outlined above are considered potential cases of drug-induced liver injury and will be considered as protocol defined criteria for withdrawal and important medical events. The investigator will arrange for the patient to return to the investigational site as soon as possible (within 24 hours of notice of abnormal results) for repeat assessment of ALT, AST, TBL and alkaline phosphatase levels, detailed history and physical examination. Patients should be followed until all abnormalities have normalized (in the investigator's opinion) or returned to the baseline state.

Elevations in ALT or AST $>3 \times$ ULN or TBL $>2 \times$ ULN alone are not considered potential cases of drug-induced liver injury, but will be followed as detailed above, within 72 hours' notice of abnormal results. If the participant cannot return to the investigational center, repeat assessments may be done at a local laboratory and the results sent to GW PVD.

12.9 Notification of Safety Information to Investigators, Regulatory Authorities and Ethics Committees.

In accordance with the EU Clinical Trials Directive³⁵, relevant parts of the FDA Code of Federal Regulations and any national regulations, GW will inform investigators, regulatory authorities and relevant IRB/ECs of all relevant safety information. This will include the reporting of relevant SAEs and all Suspected Unexpected Serious Adverse Drug Reactions (SUSARs).

This information will be provided through three sources:

- Investigator Brochure³⁶: a compilation of the clinical and non-clinical safety data available on the IMP that is relevant to the study on the IMP in human participants. The IB is updated annually.
- Development Core Safety Information: this document actually forms the Safety Section of the IB³⁶, or is updated as an appendix of the IB³⁶. This document is revised if necessary, when new important safety information becomes available (potentially up to a few times a year).
- Council for International Organizations of Medical Sciences (CIOMS) reports: these reports are issued every time a SUSAR is reported to GW. They provide information on individual case reports and are sent to all the regulatory authorities, the relevant central IRB/ECs which have approved the study and investigators. As required, the investigator should notify their regional IRB/EC of SAEs or SUSARs occurring at their site and other AE reports, i.e., CIOMS

reports and any additional safety documentation received from GW, in accordance with local procedures.

In the USA, investigators are normally required to promptly report to their IRBs all unanticipated problems involving risks to human patients, or others, including AEs that should be considered unanticipated problems. Based on current FDA guidance³² the following clarification is provided in determining what constitutes an unanticipated problem:

In general, an AE observed during the conduct of a study should be considered an unanticipated problem involving risk to human patients, and reported to the IRB, *only* if it were unexpected, serious, and would have implications for the conduct of the study (e.g., requiring a significant, and usually safety-related, change in the protocol such as revising inclusion/exclusion criteria or including a new monitoring requirement, informed consent, or IB). An individual AE occurrence *ordinarily* does not meet these criteria because, as an isolated event, its implications for the study cannot be understood.

The FDA guidance³⁷ states that, accordingly, to satisfy the investigator's obligation to notify the IRB of unanticipated problems, any investigators participating in a multicenter study may rely on the sponsor's assessment and provide to the IRB a report of the unanticipated problem prepared by the sponsor.

GW will inform investigators (regulatory authorities and applicable IRB/EC's) of any safety issues or case reports that are considered to be unanticipated and provide such reports as mentioned above. It should be noted that a single SUSAR report notified to investigators in the study does not necessarily constitute an unanticipated problem unless identified by GW in the submission cover letter.

As a minimum, the recipient will be sent all of the above and relevant updates between the period from ethics approval and final database lock.

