3.6 Clarification of Liver Function Testing

- Additional details have been included regarding follow-up of elevated liver enzyme levels that do not meet the criteria for drug-induced liver injury (DILI).
- Section 12.8 has been re-titled as the text within concerns potential cases of DILI only.
- The eligibility criterion regarding impaired hepatic function has been amended to bring into line with the criteria for DILI.

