
6.2.15 Patients who have received an IMP within the 12 weeks prior to the screening visit.

6.2.16 Any other significant disease or disorder which, in the opinion of the investigator, may either put the patient at risk because of participation in the study, may influence the result of the study, or the patient's ability to participate in the study.

6.2.17 Following a physical examination, the patient has any abnormalities that, in the opinion of the investigator would prevent the patient from safe participation in the study.

6.2.18 Patient has significantly impaired hepatic function at screening (Visit 1) or enrollment (Visit 2), defined as any of the following:

- Alanine aminotransferase (ALT) or Aspartate aminotransferase (AST) $>5 \times$ upper limit of normal (ULN).
- ALT or AST $>3 \times$ ULN **and** total bilirubin (TBL) $>2 \times$ ULN **or** international normalized ratio (INR) >1.5 .
- ALT or AST $>3 \times$ ULN with the presence of fatigue, nausea, vomiting, right upper quadrant pain or tenderness, fever, rash, and/or eosinophilia ($>5\%$).

*This criterion can only be confirmed once the laboratory results are available; patients randomized into the study who are later found to meet this criterion **must** be withdrawn from the study.*

6.2.19 Unwilling to abstain from donation of blood during the study.

6.2.20 Travel outside the country of residence planned during the study.

6.2.21 Patients previously enrolled into this study.

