10. WITHDRAWAL

In accordance with the Declaration of Helsinki³¹, the FDA regulations relating to good clinical practice (GCP) and clinical trials^{32,33,34}, the EU Clinical Trials Directive (2001/20/EC)³⁵ and/or other applicable regulations, a patient has the right to withdraw from the study at any time and for any reason without prejudice to his or her future medical care by the physician or at the institution.

The patient must be withdrawn from the study if any of the following apply:

- Administrative decision by the investigator, GW, or a Regulatory Authority.
- Pregnancy.
- Protocol deviation that is considered to potentially compromise the safety of the patient.
- Withdrawal of patient consent.
- Withdrawal of legal representative consent.
- Lost to follow up.
- ALT $>3 \times$ ULN or AST $>3 \times$ ULN **and** (TBL $>2 \times$ ULN **or** INR >1.5).
- ALT or AST $>3 \times$ ULN with the appearance of fatigue, nausea, vomiting, right upper quadrant pain or tenderness, fever, rash, and/or eosinophilia ($>5\%$).
- ALT or AST $>8 \times$ ULN.
- ALT or AST $>5 \times$ ULN for more than two weeks.
- Any other IMP is taken as part of a clinical trial during the study.

Patients may also be withdrawn from the study for any of the following:

- Patient non-compliance.
- AE, which in the opinion of the investigator, would compromise the continued safe participation of the patient in the study.
- Any evidence of drug abuse or diversion.
- Suicidal ideation or behavior of type four or five during the treatment period, as evaluated with the C-SSRS.

Should a patient request or decide to withdraw from the study, all efforts must be made to complete and report the observations as thoroughly as possible up to the date of withdrawal. Patients who withdraw should have their dose of IMP tapered gradually (10% each day) over a period of 10 days, beginning at the time the decision

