is made to discontinue. In some cases, tapering the dose of IMP may be inadvisable (e.g., continued dosing is not possible due to an AE). The decision on whether or not to taper IMP will be left to the investigator's clinical judgment. All assessments required at Visit 4 (if the withdrawal is during the blinded phase) or Visit 11 (if the withdrawal is during the OLE) should be conducted if possible. If the tapered dose is administered, patients should return for Visit 5 (if withdrawal is during the blinded phase) or Visit 12 (if the withdrawal is during the OLE) if possible. Wherever possible, the safety follow-up visit should be conducted 28 days from the date of the last dose of IMP. Patients withdrawing due to an AE should be followed up according to [Section 12.7](#). All information should be reported on the applicable CRF pages

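### Protocol Section 12.8 lists isolated ALT/AST above 8 × ULN as a liver-injury criterion, then as worded calls it not liver injury and allows 72 hours to recheck

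*Protocol*

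**What the plan says.** Section 12.8, whose title is about potential drug-induced liver injury, lists four laboratory criteria:

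1. ALT or AST above 3 × ULN, with either TBL above 2 × ULN or INR above 1.5.
2. ALT or AST above 3 × ULN with symptoms or eosinophilia.
3. ALT or AST above 8 × ULN.
4. ALT or AST above 5 × ULN persisting beyond two weeks.

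A result meeting any of them goes to the sponsor's pharmacovigilance department within 24 hours. Section 10 repeats the same four under "The patient must be withdrawn from the study if any of the following apply".

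Two paragraphs then follow the list in 12.8. One says which results are potential DILI, count as important medical events and bring the patient back within 24 hours. Its subject is "Abnormal values in AST and/or ALT concurrent with abnormal elevations in TBL" that meet the listed criteria. The other says that ALT or AST above 3 × ULN, or TBL above 2 × ULN, "alone are not considered potential cases of drug-induced liver injury, but will be followed as detailed above, within 72 hours' notice of abnormal results".

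The rationale for Amendment 1 (its Section 3.6) explains the liver changes: "Additional details have been included regarding follow-up of elevated liver enzyme levels that do not meet the criteria for drug-induced liver injury"; "Section 12.8 has been re-titled as the text within concerns potential cases of DILI only"; and "The eligibility criterion regarding impaired hepatic function has been amended to bring into line with the criteria for DILI".

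**The concern.** The two paragraphs do not match the list they are meant to serve. A value above 8 × ULN is also above 3 × ULN. If bilirubin is normal and there are no symptoms, the result meets a listed criterion, falls outside the potential-DILI sentence, and falls inside the sentence that says it is not DILI.

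At stake are the classification and the recheck time. ALT or AST above 8 × ULN is the highest transaminase threshold in the protocol and can be a patient's first abnormal result. Section 9.1.9 sends investigators to 12.8 for guidance on exactly this question. A site that follows the words could record such a result as not DILI and recheck within 72 hours, while another site, reading the title and the list, labels it potential DILI and recalls the patient within 24. The label also bears on seriousness, because Section 12.2 says that important medical events should usually be treated as serious.

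**Working it through.** The protocol gives no figure to reproduce here. The check sets each criterion against the two paragraphs below the list. The first criterion has a TBL branch and an INR branch, so the four criteria contain five triggers. All five carry the 24-hour sponsor report (Section 12.8) and mandatory withdrawal (Section 10).

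| Trigger in 12.8 | In the potential-DILI sentence? | In the 72-hour sentence? | Result as worded |
|---|---|---|---|
| (a) >3 × ULN with TBL >2 × ULN | Yes, always | No | Potential DILI, 24 h |
| (b) >3 × ULN with INR >1.5, TBL not raised | No | Not clearly, since INR is also abnormal | No stated class or return time |
| (c) >3 × ULN with symptoms or eosinophilia, TBL not raised | No | Not clearly, since another finding is present | No stated class or return time |
| (d) >8 × ULN, isolated | No | Yes, because >8 × ULN implies >3 × ULN | Not DILI, 72 h |
| (e) >5 × ULN beyond two weeks, isolated | No | Yes, because >5 × ULN implies >3 × ULN | Not DILI, 72 h |

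Count: 1 (a) + 2 (b, c) + 2 (d, e) = 5.

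Difference between the two recheck limits: 72 h − 24 h = 48 h.

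On intent, the amendment rationale says the added follow-up text is for enzyme levels that do not meet the DILI criteria. Triggers (d) and (e) are on the list under the DILI title, so the 72-hour sentence was evidently not meant for them. The same rationale says the hepatic exclusion was aligned with the DILI criteria. That exclusion (6.2.18, "Patient has significantly impaired hepatic function at screening (Visit 1) or enrollment (Visit 2), defined as any of the following") includes ALT or AST above 5 × ULN, and symptomatic elevation above 3 × ULN, neither with a bilirubin condition. This too suggests that the sponsor did not regard raised bilirubin as necessary.

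The conflict came in with Amendment 1. Under Version 1, Section 12.8 had a neutral title about reporting laboratory results and no 72-hour sentence. The amendment added the DILI title and the 72-hour sentence and kept the bilirubin-only sentence between them.

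**The case against.** A coherent reading exists. The 72-hour sentence names exactly the two components of the first criterion's bilirubin branch, so it can be taken to say that either one without the other is not potential DILI. On that reading, a value above 8 × ULN is governed by its own, more specific criterion. This is probably what the sponsor meant, but it is an inference: nothing in 12.8 states it, and the preceding paragraph, which requires the two abnormalities together, points the reader the other way.

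It can also be said that the actions that matter most are already fixed. The sponsor sees every such case within a day, the patient is withdrawn whatever the bilirubin, Section 12.2 leaves seriousness to medical judgment, Section 9.1.9 requires clinically appropriate follow-up, and Section 10 asks for the Visit 4 assessments at withdrawal where possible. All of this stands and limits the consequence. None of it supplies the label or a 24-hour recheck.

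Three narrower points also stand. Triggers (b) and (c) are a matter of silence, not contradiction. Exclusion 6.2.18 does not reproduce the 12.8 list (it has no 8 × ULN tier and no two-week duration), so it is evidence of intent only. And the counts describe wording, not frequency: the protocol gives no expected rate of such elevations, and 4:1 allocation of 20 patients puts 20 × 4/5 = 16 on active drug in the blinded phase.

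**Conclusion.** The point holds. As worded, Section 12.8 places isolated ALT or AST above 8 × ULN, and isolated elevation above 5 × ULN beyond two weeks, on its list and then excludes them from DILI. The potential-DILI sentence covers only rises with raised bilirubin. It is a drafting defect in an operative safety rule and should be fixed.

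Its size is limited to the DILI and important-medical-event label, which sites could apply differently, and to a difference of up to 48 hours in the recheck limit. That is a difference between two ceilings, not an expected delay. The clearest case is a first result above 8 × ULN with normal bilirubin. In the two-week case an earlier abnormal result is already being followed, so the label is the main issue. Reporting, withdrawal, dosing rules and the pharmacokinetic analysis do not change.

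The conclusion rests on reading the current text literally. The amendment rationale is used only to show that the literal result was not intended.

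**What to change.** Change two sentences in 12.8:

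- Make the potential-DILI sentence, with its important-medical-event status and 24-hour return, apply to any result meeting one of the four criteria listed above it. This also settles the INR and symptom/eosinophilia triggers.
- Limit the 72-hour sentence to elevations that meet none of those criteria.

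Optionally, name prothrombin time/INR and the white-cell differential in the repeat panel. Prothrombin time and the differential are already in Table 9.1.9-1, and they are largely covered by the Visit 4 assessments due at withdrawal, so this is not essential.

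The cost is two sentences in an amendment, with no new visit, assay or analysis.

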13. STATISTICAL CONSIDERATIONS

A statistical analysis plan (SAP) will be produced prior to the database lock and analysis of the study. Any deviations from the original SAP will be described in the final clinical study report.

13.1 Sample Size, Power and Significance Levels

A total of 20 patients will be enrolled in this study. There is no formal sample size: Calculation and analysis is descriptive only.

13.2 Interim Analysis

An interim analysis will be conducted at the end of the Double Blind phase of the study and may also be considered during the OLE phase, if long term data is required to support New Drug Application/Marketing Authorization Application submissions.

13.3 Analysis Sets

13.3.1 Safety Set

All subjects who are treated and receive at least one dose of IMP will be included.

The Safety set is the primary analysis set for all safety endpoints.

13.3.2 Pharmacokinetic Analysis Set

All subjects who are treated and receive at least one dose of IMP and who provide some on-treatment data will be included.

The PK analysis set is the primary analysis set for all PK endpoints.

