8. TREATMENT PROCEDURES

8.1 Investigational Medicinal Product Dosage, Administration and Schedule

The IMP will consist of three types of medication:

- GWP42003-P Oral Solution containing 100 mg/mL CBD.
- Placebo Oral Solution containing excipients.
- Clobazam (patient supplied).

The GWP42003-P/placebo will be presented as an oral solution containing either the active pharmaceutical ingredient and excipients (in the case of GWP42003-P) or only excipients (in the case of placebo). For details regarding GWP42003-P/placebo formulations, see [Section 5](#).

All patients will be weighed during the study visits and the daily volumes of GWP42003-P/placebo solution to be taken during the titration period, and for the remainder of the study, will be calculated and provided to the patient and/or caregiver. Further information on dispensing procedures will be provided in a separate Pharmacy Manual.

Each patient will take their first dose of GWP42003-P/placebo at Visit 2, Day 2 in the clinic. Patients not entering the OLE will take their final maintenance dose of GWP42003-P/placebo at Visit 4 (Day 33) in the clinic. Patients entering the OLE will take their final dose of IMP at Visit 11 (one year after the end of the blinded phase of the study) or sooner (if marketing authorization is granted within one year).

Patients will use their own supply of Clobazam throughout the study. Patients will continue on the dose that they were on at screening for the blinded phase of the study. Clobazam will only be an IMP for the blinded section of the study.

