8.1.2 Dose Escalation and Dose Adjustments

Patients will enter the blinded phase of the study and will be up-titrated over ten days (Day 2 to Day 11) to a maintenance dose or equivalent of GWP42003-P/placebo of 20 mg/kg/day. If GWP42003-P is not tolerated then the dose can be reduced accordingly at the discretion of the investigator. The titration regimen is described in [Table 8.1.2-1](#).

Table 8.1.2-1 Dose Up-Titration Regimen*		
Day - GWP42003-P/Placebo (Blinded Period)	Day - GWP42003-P only (OLE**)	Dose Level (GWP42003-P or equivalent placebo)
2	34	2.5 mg/kg
3	35	2.5 mg/kg
4	36	5.0 mg/kg
5	37	5.0 mg/kg
6	38	7.5 mg/kg
7	39	7.5 mg/kg
8	40	10.0 mg/kg
9	41	10.0 mg/kg
10	42	15.0 mg/kg
11	43	15.0 mg/kg
12 onwards	44 onwards	20.0 mg/kg

*GWP42003-P /placebo is to be taken twice daily. Total daily doses are shown.

** Only patients who were taking placebo during the double-blind period will up-titrate according to this schedule during the OLE period. Those taking GWP42003-P during the double-blind period will down-titrate their blinded IMP whilst simultaneously up-titrating with GWP42003-P, thus maintaining a daily dose of 20 mg/kg/day GWP42003-P throughout.

The titration regimen defined above should be followed to the maximum dose (20 mg/kg/day). Should an AE occur during titration which is attributable to IMP or concomitant AED, then IMP dose should be reduced to the next lower dose. Any other changes in concomitant AED therapy should be reviewed with the medical monitor before being initiated.

For those patients who do not enter the OLE the dose of GWP42003-P/placebo will taper off over 10 days beginning on Day 34. The patient will reduce the dose by 10% of the maintenance dose each day and treatment will end on Day 43.

Patients who enter the OLE period will be transitioned to the OLE treatment over a 10-day period in order to maintain blinding, simultaneously down-titrating blinded GWP42003-P /placebo whilst up-titrating open-label GWP42003-P. As such, patients who were taking GWP42003-P during the blinded period will maintain their 20 mg/kg/day dose throughout the transition from the blinded period into the OLE period and patients who received placebo during the blinded period up-titrate slowly to the 20 mg/kg/day dose in the OLE period. After this has taken place, the

maintenance dose of GWP42003-P may be adjusted up or down at the discretion of the investigator to a maximum of 30 mg/kg/day (no minimum).

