8.2 Concomitant Therapy

Doses of any concomitant AEDs, including CLB, must have been stable for at least four weeks prior to screening and must remain stable throughout the blinded phase of the study. If there are symptoms of toxicity suspected to be from a drug interaction, the investigator may adjust GWP42003-P/placebo or the CLB or other AEDs after discussion with the medical monitor.

The use of rescue medication is allowed if necessary. The use of oxygen may be considered as rescue medication if used as required. Any medication, other than the IMP, taken during the study must be recorded on the Case Report Form (CRF).

Any non-pharmacological therapies (e.g., ketogenic diet, VNS) must also be stable up to four weeks prior to baseline and throughout the duration of the study.

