8.3 Prohibited Therapy During Study Period

The following medications are prohibited for the duration of the study starting from acquisition of patient consent. However, any patients taking these medications after screening should not be withdrawn from the study unless there are safety concerns. If applicable, the possible effects of these medications on the primary endpoint will be considered.

- Any new medications or interventions for epilepsy (including ketogenic diet and VNS) or changes in dosage.
- Patients should not take any more than three AEDs inclusive of CLB.
- Recreational or medicinal cannabis or synthetic cannabinoid based medications (including Sativex) within three months prior to or during the study.

If any other IMP is taken as part of a clinical trial within twelve weeks of the screening visit or during the study, the patient must be withdrawn from this study.

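### The CLB dose may be changed because of a suspected interaction, but the primary PK comparison takes no account of the CLB dose taken

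*Protocol*

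**What the plan says.** Section 13.3.2 defines the PK set: "All subjects who are treated and receive at least one dose of IMP and who provide some on-treatment data will be included". It adds: "The PK analysis set is the primary analysis set for all PK endpoints". No condition is set on the CLB dose, the GWP42003-P dose reached, or time on maintenance.

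On the CLB dose, Section 8.1 states: "Patients will continue on the dose that they were on at screening for the blinded phase of the study". Section 8.2 also starts from stable doses. It then provides that, where toxicity from a drug interaction is suspected, "the investigator may adjust GWP42003-P/placebo or the CLB or other AEDs after discussion with the medical monitor". Section 8.3 lists changes in dosage of epilepsy treatment as prohibited, but says that "any patients taking these medications after screening should not be withdrawn from the study unless there are safety concerns", and that possible effects on the primary endpoint will be considered.

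The GWP42003-P dose may change too. Section 8.1.2 says: "If GWP42003-P is not tolerated then the dose can be reduced accordingly at the discretion of the investigator". For withdrawals, Section 10 says: "Patients who withdraw should have their dose of IMP tapered gradually (10% each day) over a period of 10 days". It also asks, if possible, for "All assessments required at Visit 4 (if the withdrawal is during the blinded phase"), and Visit 4 includes the PK profile.

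The version 2 synopsis (Statistical Considerations) gives the analysis. It is a log-scale mixed model with treatment (CLB, or CLB plus GWP42003-P) as fixed effect and subject as random effect, applied to Cmax and both AUCs. A lack of meaningful effect is declared if the 90% CI of the geometric mean ratio lies within 0.5 to 2.0.

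**The concern.** The Day 1 to Day 33 ratio isolates the effect of GWP42003-P on CLB and N-CLB only if the CLB dose is the same on both days. Section 8.2 allows that dose to change, and the trigger is the effect the trial measures. The patients most likely to have CLB lowered are those whose exposure rose most. They stay in the study and in the primary set, and neither the set nor the model corrects for the lower dose. An interaction near the upper bound could then be reported as a lack of meaningful effect, and a reader would use that conclusion when combining the two drugs.

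**Working it through.** **Inputs from the protocol.** The protocol gives no sample-size or power figure to reproduce.
- Allocation (Section 7.2, N = 20): 20 × 4/5 = 16 on GWP42003-P and 4 on placebo.
- Decision rule: the whole 90% CI must lie within 0.5 to 2.0, so the nominal error at each bound is (1 − 0.90)/2 = 5%.
- CLB takes up to 14 days to reach steady state (Amendment 1, Section 3.1).

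**Assumptions, not in the documents.**
- Exposure is proportional to the CLB dose.
- CLB is halved in the k strongest responders of 16.
- The between-patient SD of the log ratio is 0.3 (0.5 as an alternative).
- The within-patient log SD is 0.25 per occasion.
- The true ratio R lies between 1.0 and 3.0.

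**Step 1: the expected ratio.** Observed ratio = R × 0.5^(k/16).

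| R | k=2 | k=4 | k=6 |
|---|---|---|---|
| 1.0 | 0.92 | 0.84 | 0.77 |
| 2.0 | 1.83 | 1.68 | 1.54 |
| 2.5 | 2.29 | 2.10 | 1.93 |
| 3.0 | 2.75 | 2.52 | 2.31 |

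With a reduction to 75% of the dose instead of 50%, R = 2.0 becomes 1.93, 1.86 and 1.80.

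**Step 2: the decision.** The rule uses the interval, so the expected ratio alone does not settle it. The check simulated 40,000 trials of 16 paired log ratios, each with a t-based 90% CI. The table shows the chance of declaring no effect at SD 0.3.

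| R | dose-normalised | k=2 | k=4 | k=6 |
|---|---|---|---|---|
| 1.5 | 76% | 94% | 99% | >99% |
| 1.75 | 29% | 61% | 85% | 96% |
| 2.0 | 5% | 21% | 47% | 74% |
| 2.25 | 0.5% | 3.7% | 15% | 37.5% |
| 2.5 | <0.1% | 0.4% | 2.7% | 12% |
| 3.0 | 0% | 0% | about 0% | 0.4% |

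At R = 2.0 with SD 0.5, the chance is 5% normalised and 18%, 40% and 64% as planned. For R below 2.0 the declaration is not false under the protocol's own margin, but it is made far more often than the data justify. From 2.0 upwards it is false.

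**Step 3: why a point estimate below 2.0 is not enough.** Take R = 2.2 in every patient, with no other variability. With k = 3 the ratio is 2.2 × 0.5^(3/16) = 1.93, with 90% CI 1.71 to 2.18. With k = 4 it is 1.85, with 90% CI 1.61 to 2.12. Neither would be declared no effect.

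**Step 4: analysing only patients with an unchanged CLB dose.** At R = 2.0, dropping the four strongest responders gives an expected ratio of 1.77 (SD 0.3) or 1.64 (SD 0.5). This subset is itself biased towards no effect.

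**The case against.** The strongest reply is that this belongs to the SAP. Section 13 promises one before database lock, Section 13.3.3 foresees exclusions from the analysis populations, and Section 8.3 says effects on the primary endpoint will be considered. The version 2 text of Section 13.6.3 is also not in the text at hand. The absence of a dose term is read from the version 2 synopsis, the version 1 section and the amendment's listed changes. That caveat stands. But the protocol does fix the primary PK set and the model terms, and none of the three sections gives a rule that would handle a changed CLB dose.

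Sections 8.1 and 8.2 can be read as a general rule and a safety exception. Even so, the analysis follows only the rule.

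The frequency and size of CLB changes are unknown. Section 8.2 requires symptoms and a discussion with the medical monitor, and names other drugs that could be adjusted instead. This stands in full, so the figures above are conditional.

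A reader might infer that withdrawal or taper profiles will be pooled with Day 33. The documents do not say so. Section 13.3.2 defines subjects, not profiles; the second PK assessment is defined as Day 33 after 21 days of maintenance; and PK at withdrawal is asked for only if possible. What remains is that no text rules pooling out.

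**Conclusion.** The point holds in a limited form. As written, the plan lets a CLB dose change prompted by the interaction pass uncorrected into the primary ratio. Under the assumptions above, the error at a true ratio of 2.0 rises from 5% to between 18% and 74% when 2 to 6 of 16 doses are halved. The verdict is at risk mainly for true ratios of about 1.5 to 2.5, and only if such changes occur.

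Three stronger readings are not supported:
- **An observed ratio below 2.0 flips the conclusion.** The rule needs the whole interval inside the bounds, and Step 3 shows it can fail to be.
- **A large interaction would be missed.** At a true ratio of 3.0 the estimate is diluted, but the verdict hardly changes (at most about 1%, with six halved at SD 0.5).
- **The bias always runs towards no effect, or serves a wished-for result.** With no true interaction, four halved doses move the ratio from 1 to 0.84. The hypothesis in Section 3.4 is that exposure may go either way.

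**What to change.** - **Sections 8.1 and 8.2:** reconcile the two statements on the CLB dose in the blinded phase. Which one should govern is a clinical matter and is not proposed here.
- **Sections 13.3.2 and 13.6.3, primary comparison:** analyse CLB and N-CLB Cmax and AUC normalised to the mg of CLB taken at that visit. CLB dose is already recorded in the diary and by the investigator. The cost is an assumption of dose proportionality, to be stated.
- **On-treatment profile:** define it as the Day 33 visit on GWP42003-P/placebo maintenance. List separately, and do not pool, profiles from early-withdrawal or taper visits, or within 14 days of a CLB dose change. Report how many there are and why. CLB normalisation cannot repair a reduced or tapered GWP42003-P dose or a profile before steady state. The cost is the loss of a few profiles, which may come from strong responders, so the reasons must be visible.
- **Sensitivity analysis:** show the unchanged-CLB-dose analysis as such, noting that it can drop the strongest responders. It should not be a condition for the no-effect claim.

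The analysis changes are wording in two sections and need no new data.
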